1 BACKGROUND

KAPT Block:

The King's Mill Anterior-Posterior and Transverse (KAPT) Block, first described in 2015 and presented in 2016, represents a significant advancement in the field of pain management for gynaecological procedures, particularly outpatient hysteroscopy. This type of paracervical block specifically targets the Lee-Frankenhauser (LF) plexus, a part of the Inferior Hypogastric Plexus (IHP), within the Uterosacral Ligament Complex (USLC). The KAPT Block is strategically applied 1.65-3.3cm distal to the cervical insertion of the USLC, a region dense with nerve fibers. Its precise application effectively denervates the cervix and fundus by transecting the LF plexus under the terminal 2.5cm of the USLC.

The efficacy of the KAPT Block was first demonstrated in a prospective observational study presented at the RCOG World Congress in 2016. In this study involving 37 patients, the KAPT Block showed promising results with a mean pain score of 0.704/10 (SD ± 0.24) for Myosure® procedures and 1.2/10 (SD ± 0.44) for Novasure. Importantly, no procedures had to be abandoned due to pain.

A subsequent prospective study with 73 patients (53 undergoing Myosure® and 20 Novasure® procedures) confirmed these findings. The study reported a mean pain score of 0.41/10 for Myosure® and 0.8/10 for Novasure. Notably, a significant proportion of these patients were pre-menopausal and suffered from dysmenorrhea, highlighting the block's effectiveness across various patient profiles.

Paracervical block:

Paracervical block (PCB) is a widely used local anaesthetic technique in outpatient hysteroscopy, but no single method has been established as unequivocally superior. Despite some uncertainty in the literature regarding its superiority, a meta-analysis of 20 trials involving 2851 participants indicated that paracervical injection significantly reduced pain in women undergoing hysteroscopy as outpatients. Intracervical and paracervical injections of local anaesthetic were found to be effective, while transcervical and topical applications did not show significant pain reduction. The meta-analysis supported the conclusion that paracervical local anaesthetic injection is the best method for pain control in outpatient hysteroscopy. However KAPT Block was not included in this meta-analysis

SHORT TITLE/ACRONYM

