5.2 Outcome

- 1. **Pain Score Comparison**: Determination of differences in pain scores between the KAPT Block and Paracervical Block at three key stages: during cervical dilatation, throughout the hysteroscopy procedure, and 10 minutes post-procedure.
- 2. **Patient Comfort Analysis:** Assessment of patient comfort levels and procedural tolerability with each anaesthetic technique, contributing to patient-centred care in outpatient settings.
- 3. **Clinical Efficacy Evaluation**: Evaluation of the clinical efficacy of each block technique, aiding in evidence-based decision-making for pain management in outpatient hysteroscopy.

6 STUDY DESIGN and METHODS of DATA COLLECTION AND DATA ANALYIS

This study will be a randomized control trial, comparing the efficacy of KAPT Block and Paracervical Block in outpatient hysteroscopy. This approach will provide robust, comparative data on the effectiveness of these anaesthetic techniques.

Data Collection Methods:

Patient Questionnaires with Visual Pain Score: Patients will complete questionnaires with a
visual analogue scale (VAS) to self-report their pain levels at various stages of the procedure
(during cervical dilatation, the procedure itself, and 10 minutes post-procedure). This method
allows for direct, objective assessment of pain from the patient's perspective.

Data Analysis Methods:

Quantitative Analysis: The collected pain scores will be statistically analysed to determine the
effectiveness of each anaesthetic technique. This analysis will involve comparing mean pain
scores and assessing variations in pain experiences among patients.

Data Management:

- Data will be de-identified to maintain patient confidentiality.
- Electronic data will be securely stored and encrypted. Only authorized personnel will have access.
- Hard copies, if any, will be kept in a secure location.
- After the study, data will be archived as per institutional and legal guidelines.

Software: Statistical software will be used for quantitative data analysis.

7 - Patient Public Involvement (PPI)PPI groups have been involved with the study proposal process. A number of patients were asked specific questions regarding the study design and purpose. All information has been stored for future reference and publication.

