8.2.2 Sampling technique

Participants will be selected randomly from women attending outpatient hysteroscopy at Kings Mill Hospital. This random sampling approach ensures that the sample is representative of the population receiving these procedures. This strategy aligns with the study's methodological framework, allowing for a fair comparison between the two anaesthetic techniques without bias, and it is reflective of the theoretical framework focusing on pain management in outpatient gynaecological procedures.

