8.3 Recruitment

The recruitment process for the study involves identifying and enlisting participants who meet the eligibility criteria. Women attending outpatient hysteroscopy procedures at Kings Mill Hospital will be screened for eligibility. This screening will include verifying their age (18 years and above), assessing for any contraindications to the local anaesthetics used in the study, and ensuring they are willing and able to provide informed consent. Participants will receive a patient information leaflet about the study along with their appointment letter, sent at least one week before their scheduled procedure. This ensures they have ample time to consider participation. The information leaflet will detail the study's purpose, risks, benefits, and what participation entails. Consent will be obtained from those who agree to participate when they attend their appointment, ensuring informed decision-making. Those who agree to participate will then be enrolled in the study and randomly assigned to either the KAPT Block or Paracervical Block group.

** stratify here

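### Self-reported pain is called objective and the comparison free of bias, but the protocol does not say whether the patient, or whoever hands over the questionnaire, is kept unaware of the block

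*Protocol*

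**What the plan says.** Section 6 (Data Collection Methods) has patients complete a questionnaire with a "visual analogue scale (VAS) to self-report their pain levels at various stages of the procedure". The stages are cervical dilatation, the procedure itself and 10 minutes afterwards. The same paragraph says that this "allows for direct, objective assessment of pain", qualified as being from the patient's perspective.

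Section 8.2.2 describes random selection of participants and presents it as "allowing for a fair comparison between the two anaesthetic techniques without bias".

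Section 8.3 has consent taken at the appointment, and then: "Those who agree to participate will then be enrolled in the study and randomly assigned to either the KAPT Block or Paracervical Block group". The Study Summary has the questionnaire handed over during and after the procedure, without saying by whom.

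Section 1 introduces the new technique as "The King's Mill Anterior-Posterior and Transverse (KAPT) Block, first described in 2015 and presented in 2016", and says that it "represents a significant advancement in the field of pain management". Section 8 places the whole trial at Kings Mill Hospital.

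The text shown does not mention blinding, masking or concealment of allocation for anyone, and gives no reason for an open design.

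**The concern.** A pain rating made by the patient is a subjective outcome, and it can move with what she expects of the treatment she believes she received. Calling it objective suggests that the measurement needs no protection, when this kind of measurement needs it most. The claim of freedom from bias rests on random sampling. Sampling bears on whom the results represent, and random assignment bears on whether the groups are alike at the start. Neither acts on how pain is reported once the block is known.

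This matters here for three reasons. The VAS is the only outcome with a named instrument, and section 9.4 calls the questionnaire the basis of the research. Consent takes place at the appointment, assignment follows it, and pain is scored during and after the procedure, so there are several moments at which the arm could be disclosed before a score is given. And blinding governs conduct in the room, so a statistical analysis plan cannot supply it afterwards. If a difference is found, the trial could not tell a better block from a better-regarded one.

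**Working it through.** **1. Reading the relevant sections against each other**

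| Question | Where an answer would stand | What is there |
|---|---|---|
| Is the outcome subjective? | Section 6 | Yes, self-report on a VAS, but labelled objective |
| Is the patient unaware of the block? | Sections 6 and 8.3 | Not addressed |
| Is the person handing over the form unaware? | Study Summary, section 6 | Person not identified, awareness not addressed |
| Is allocation concealed until consent? | Section 8.3 | Assignment follows consent; concealment not addressed |
| What supports the claim of no bias? | Section 8.2.2 | Random sampling only |
| Do the arms differ in ways that can be noticed? | Section 4, Technique | Yes: Pipelle measurement, a tenaculum and a pause of at least 3 minutes are described only for KAPT |
| Are the blocks described neutrally? | Sections 1 and 3 | KAPT is called a significant advancement and sophisticated; paracervical block is also praised, as the best method according to a meta-analysis and as a preferred method |

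**2. Illustration of size**

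The protocol gives no figure for reporting bias, so there is none to reproduce. The size of the shift below is assumed.

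Inputs:
- Total of 48 patients, 10% dropout and alpha 0.05 (section 8.2.1).
- 1:1 allocation and a two-sided test. Both are assumed, since neither is stated.
- Evaluable patients: 48 × 0.90 = 43.2, or 21.6 per arm, rounded up to n = 22.
- True difference between blocks: zero.
- Reporting shift between arms: b = 0.2, 0.3 or 0.5 SD (assumed).

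Formula: the two-sample t statistic has 2n − 2 = 42 degrees of freedom and non-centrality b × √(n/2) = b × √11 = b × 3.317. The critical value is 2.018. The chance of a significant result is P(|T| > 2.018).

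| b (SD) | Non-centrality | n = 22 per arm | n = 24 per arm (no dropout) |
|---|---|---|---|
| 0 | 0 | 5.0% | 5.0% |
| 0.2 | 0.663 | 9.9% | 10.4% |
| 0.3 | 0.995 | 16.3% | 17.4% |
| 0.5 | 1.658 | 36.7% | 39.6% |

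The non-centrality column is for n = 22. A normal approximation at 21.6 per arm gives 10%, 17% and 38%, so the choice of method matters little.

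**3. What the table shows**

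The false-positive rate is higher at 24 per arm than at 22. For a fixed shift it rises with sample size, so recruiting more patients would not remove the problem. The protection has to come from conduct.

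**The case against.** The best case for the protocol runs as follows.

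- *Silence is not an open design.* This stands. The protocol does not say that patients are told their block, nor what the person handing over the form knows. The patient leaflet and consent pages are not shown. A reader might infer that the trial is unblinded by design or that the questionnaire is handed over by someone who knows the arm. The text supports only that blinding is not addressed.
- *The VAS is not the only outcome.* This stands. Section 5.2 also lists patient comfort and tolerability, and clinical efficacy, and the schedule in Appendix 2 lists an interview. The VAS is, however, the only outcome instrument named.
- *The direction of bias is not shown.* This largely stands. Both arms receive an active injection, and nothing says what patients expect of either. A reader might infer from the block's name that the hospital developed and promotes it, but the protocol does not say who developed it. The favourable wording is background text that patients may never see, and paracervical block is praised too. A bias towards KAPT is plausible, no more.
- *The word objective is qualified as being from the patient's perspective.* The qualifier concedes that the rating is personal, but does not make it objective.
- *The claim of no bias concerns sampling.* That is where it stands, but it is attached to the comparison of the two techniques, which random sampling does not protect.
- *Patient blinding may fail, because the steps differ.* This is a fair limit on any remedy. It is a reason to state what is attempted and what remains, rather than to leave the matter out.

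**Conclusion.** The point holds in this form: the main patient-reported outcome is wrongly described as objective, the comparison is wrongly described as free of bias on the strength of random sampling, and the protocol does not say whether the patient or the person handing over the form is kept unaware of the block. As written, nothing prevents disclosure before scoring, and expectation could bias the result in a way that no later analysis can repair.

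The figures of about 10%, 16% and 37% rest on assumed shifts of 0.2, 0.3 and 0.5 SD, 1:1 allocation, a two-sided test, 22 evaluable patients per arm and no true difference. They show how sensitive the trial would be to such a shift; they are not evidence that one will occur. A reader might also blame the small sample, but systematic bias cannot be separated from a true effect at any sample size.

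The change should be made before recruitment. It is cheap, and attempting to blind the patient is feasible without a sham because both arms receive real local-anaesthetic injections.

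**What to change.** In section 6, state that patients are blinded to allocation as far as practicable, and say how:

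- The leaflet describes both blocks neutrally.
- Allocation is opened only by the operator, after consent.
- The block is not named to the patient before the 10-minute score.
- The VAS form carries a study number but no arm.
- Where existing staffing allows, the form is handed over by someone who has not been told the arm.

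In the same section, replace *objective* with *patient-reported*. In section 8.2.2, delete the claim that the comparison is without bias.

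State as limitations that the operator is unblinded and that the differing steps described under Technique may reveal the arm to an awake patient. If patient blinding is judged infeasible, say so and give the reason. A question at the end of the visit on which block the patient thinks she received is optional.

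The cost is revised wording in the protocol and leaflet and a form without the arm, with no extra staff. The downside is some care over what is said in the room, and blinding that may be imperfect. No dose or clinical rule is affected.

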8 STUDY SETTING

The study will be conducted at Kings Mill Hospital, which has a significant number of outpatient hysteroscopy procedures annually. This setting provides an ideal environment to evaluate and compare the effectiveness of the KAPT Block and Paracervical Block in pain management.

SAMPLE AND RECRUITMENT Eligibility Criteria

4

SHORT TITLE/ACRONYM

8.1 Inclusion criteria

- Women attending outpatient hysteroscopy procedures at Kings Mill Hospital.
- Age 18 years and above.
- Willing to participate and able to provide informed consent.

8.1.2 Exclusion criteria

- Women with known contraindications to local anaesthetics.

- Women with a history of allergic reactions to the anaesthetics used.

8.2 Sampling

8.2.1 Size of sample

The sample size is based on previous studies indicating a significant difference in pain scores between different anaesthetic techniques. Prior research by Noor et al. (2021) showed a noticeable variation in pain scores with a relatively small sample. Our study aims for a sample size of 48 patients, considering a 10% increase to account for potential dropout. This size is determined to achieve adequate power (80%) and a significant level (α error = 0.05), ensuring the study is sufficiently powered to detect meaningful differences in pain scores between the KAPT Block and Paracervical Block.

8.2.2 Sampling technique

Participants will be selected randomly from women attending outpatient hysteroscopy at Kings Mill Hospital. This random sampling approach ensures that the sample is representative of the population receiving these procedures. This strategy aligns with the study's methodological framework, allowing for a fair comparison between the two anaesthetic techniques without bias, and it is reflective of the theoretical framework focusing on pain management in outpatient gynaecological procedures.

8.3 Recruitment

The recruitment process for the study involves identifying and enlisting participants who meet the eligibility criteria. Women attending outpatient hysteroscopy procedures at Kings Mill Hospital will be screened for eligibility. This screening will include verifying their age (18 years and above), assessing for any contraindications to the local anaesthetics used in the study, and ensuring they are willing and able to provide informed consent. Participants will receive a patient information leaflet about the study along with their appointment letter, sent at least one week before their scheduled procedure. This ensures they have ample time to consider participation. The information leaflet will detail the study's purpose, risks, benefits, and what participation entails. Consent will be obtained from those who agree to participate when they attend their appointment, ensuring informed decision-making. Those who agree to participate will then be enrolled in the study and randomly assigned to either the KAPT Block or Paracervical Block group.

** stratify here

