2. RATIONALE	
3. THEORETICAL FRAMEWORK	
4. RESEARCH QUESTION/AIM(S)	
5. STUDY DESIGN/METHODS	
6. STUDY SETTING	
7. SAMPLE AND RECRUITMENT	
8. ETHICAL AND REGULATORY COMPLIANCE	
9. DISSEMINATION POLICY	
10. REFERENCES	
11. APPENDICES	

SHORT TITLE/ACRONYM

KEY STUDY CONTACTS

Chief Investigator	[contact]		
Study Co-ordinator	[name]		
	[contact]		
Sponsor	Sherwood Forest Hospitals NHS Foundation Trust.		
Joint-sponsor(s)/co-sponsor(s)	None		
Funder(s)	None		
Key Protocol Contributors	[name] [contact]		
Committees			

STUDY SUMMARY

Study Title	Comparative Analysis of Pain Relief between KAPT Block and Paracervical Block for Outpatient Hysteroscopy Procedures at Kings Mill Hospital	
Internal ref. no. (or short title)	The KAPT-Para Block Trial	-
Study Design	48 patients attending outpatient hysteroscopy, divided into two groups. One group will have Paracervical block, the other group will have KAPT block. Questionnaire will be handed over during and after the procedure to assess the pain scores.	
Study Participants	Patients having outpatient hysteroscopy procedures	-
Planned Size of Sample (if applicable)	48 patients divided in to two groups	-
Follow up duration (if applicable)	N/A	_
Planned Study Period	6 MONTHS from 1 st patient recruitment. September 2024.	-
Formal study end date	January 2025 after all data is collected and analysed.	Commented [ST(FHNFT1]: @[name]
Research Question/Aim(s)	Which local anaesthetic provided more pain relief for outpatient hysteroscopy procedures.	

SHORT TITLE/ACRONYM

ROLE OF STUDY SPONSOR AND FUNDER

ROLES AND RESPONSIBILITIES OF STUDY MANAGEMENT COMMITEES/GROUPS & INDIVIDUALS

PROTOCOL CONTRIBUTORS

[figure not shown]
KEY WORDS:

- 1. Outpatient Hysteroscopy Pain Management
- 2. KAPT Block in Gynaecological Procedures
- 3. Paracervical Block Efficacy
- 4. Local Anaesthesia in Hysteroscopy
- 5. Comparative Analgesia in Gynaecology
- 6. Pain Relief Techniques in Outpatient Gynaecological Procedures

STUDY FLOW CHART

Aim: To determine which method, KAPT Block or Paracervical Block, offers superior pain relief at critical stages of the outpatient hysteroscopy procedure: during cervical dilatation, throughout the procedure, and 10 minutes post-procedure. This will involve a detailed analysis of pain scores at these specific time intervals.

SHORT TITLE/ACRONYM

SHORT TITLE/ACRONYM

STUDY PROTOCOL

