5 RESEARCH QUESTION/AIM(S)

How do the pain relief outcomes of the King's Mill Anterior-Posterior and Transverse (KAPT) Block compare to the Paracervical Block in women undergoing outpatient hysteroscopy procedures **5.1 Objectives**

- To conduct a randomised control trial evaluating and comparing the pain scores of women undergoing outpatient hysteroscopy when administered either the KAPT Block or the Paracervical Block.
- 2. To determine which method, KAPT Block or Paracervical Block, offers superior pain relief at critical stages of the outpatient hysteroscopy procedure: during cervical dilatation, throughout the procedure, and 10 minutes post-procedure, through detailed analysis of pain scores at these specific intervals.

The out patients hysteroscopy procedures will include:

Myosure removal of polyps

Myosure removal of fibroids

Thermablate endometrial ablation

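### Section 8.3 leaves stratification as an unfinished note, and Sections 5.1 and 8.1 do not clearly define the same population; the likely cost is precision and credibility, not bias

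*Protocol*

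**What the plan says.** **Allocation.** Section 8.3 says that consenting women will be "randomly assigned to either the KAPT Block or Paracervical Block group". The next and last line of that section is "stratify here". The protocol names no factor, levels, allocation ratio or method of restriction. The Study Summary gives only "48 patients divided in to two groups".

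**Population.** Section 8.1 includes "Women attending outpatient hysteroscopy procedures at Kings Mill Hospital", aged 18 or over and able to consent, with no condition on the procedure. Section 5.1 says "The out patients hysteroscopy procedures will include", followed by Myosure for polyps, Myosure for fibroids and Thermablate endometrial ablation.

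**Pain by procedure.** Section 1 reports two KAPT series. The first (37 patients) gives means of 0.704 (SD 0.24) for Myosure and 1.2 (SD 0.44) for Novasure. The second (73 patients: 53 Myosure, 20 Novasure) gives a "mean pain score of 0.41/10 for Myosure® and 0.8/10 for Novasure".

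**Analysis and size.** Section 6 plans a comparison of mean pain scores. Section 8.2.1 sets 48 patients for 80% power at alpha 0.05, "considering a 10% increase to account for potential dropout", without stating an effect size or SD.

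**The concern.** The note in Section 8.3 shows that stratification was meant and never specified. This cannot wait for a statistical analysis plan, because the factor determines how the allocation list is built and must be fixed before the first woman is randomised.

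Procedure type is the likely candidate. It should be known before allocation, and it is the one factor for which the protocol itself prints different pain scores. In a trial of this size the two arms can differ by chance in their share of ablations. If ablation hurts more, such a difference adds noise to the comparison and leaves a reader unsure what an observed difference means.

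The unclear population bears on the same question. Strata cannot be defined until the protocol says whether the three procedures in Section 5.1 are the whole trial or only examples. A recruiter faced with a woman booked for another hysteroscopy cannot tell from the text whether she is eligible.

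**Working it through.** **1. The plan's own figure.** The 48 cannot be reproduced, because no effect size or SD is given. It fits a base of 43 evaluable patients: 43/0.9 = 47.8 and 43 × 1.1 = 47.3, both rounding up to 48. Solving backwards at two-sided 0.05 (sidedness is not stated, so this is assumed) and 80% power, the detectable difference is (1.960 + 0.842) × √(2/n) SD: 0.81 SD at 24 per arm and 0.84 SD at 22 per arm.

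**2. Gap between procedures** (Section 1, Novasure minus Myosure). First series: 1.2 − 0.704 = 0.496. Second series: 0.8 − 0.41 = 0.39.

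**3. Chance imbalance.** Inputs: 24 per arm (48/2; equal allocation is inferred) and an ablation share of 20/73 = 0.274 (assumed to carry over from the second series).
- SD of the between-arm difference in share: √(2 × 0.274 × 0.726/24) = 0.129. The 95% limit is 1.96 × 0.129 = 0.25.
- Shift in the arm difference at that limit: 0.253 × 0.39 = 0.10 and 0.253 × 0.496 = 0.13 points.
- With about 21.5 per arm after 10% loss, the SD is √(2 × 0.274 × 0.726/21.5) = 0.136, and the shifts are again 0.10 and 0.13.
- With 13 ablations among 48 patients, the hypergeometric probability of an imbalance of at least 20 percentage points is 19%. With 24 ablations among 48 it is 15%.

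**4. Variance due to procedure.** With share p, gap d and the printed SDs:
- Within: 0.726 × 0.24² + 0.274 × 0.44² = 0.0949, so SD 0.308.
- Between: p(1 − p)d² = 0.199 × 0.496² = 0.0489.
- Total: 0.1438, so SD 0.379. Procedure accounts for 0.0489/0.1438 = 34% of the variance, or 24% with d = 0.39. Section 1 prints no SD for the second series, so pairing d = 0.39 with these SDs is an assumption.

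**5. Power after stratifying and adjusting.** Take the effect that the unadjusted 24 v 24 comparison detects with 80% power and remove the between-procedure variance. Power is then Φ(2.80 × total SD/within SD − 1.96). For d = 0.496 and p = 0.274: 2.80 × 0.379/0.308 − 1.96 = 1.49, giving 93%. The table covers ablation shares of 27% and 50%. The shift column uses the 95% limit at each share (25 and 29 percentage points).

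| Within-procedure SD | Power after adjustment | 95% shift as share of detectable difference |
|---|---|---|
| 0.24 and 0.44 (printed) | 89-93% | 34-41% |
| 1 point (assumed; gap 0.496) | about 82% | 15-17% |
| 2 points (assumed) | 80-81% | 6-9% |

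**6. Type I error without stratification** (40,000 simulated trials per setting, gap 0.496, unadjusted t-test). Overall it is 4.9-5.0%. Among trials with an imbalance of at least 20 percentage points it is 13-15% with the printed SDs, 6-7% with SD 1 and about 5% with SD 2.

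**The case against.** Four counter-arguments deserve weight.

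*The evidence is indirect.* The pain gap is for Novasure in KAPT patients only. The trial lists Thermablate, and nothing is given by procedure for the paracervical block. This stands: the gap is an assumption for this trial. It supports choosing procedure as the factor but does not establish the size of the benefit.

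*The gap is small.* A reader might take the ratios 1.2/0.704 = 1.70 and 0.8/0.41 = 1.95 to mean that procedure dominates pain. These are ratios of scores near zero, and the absolute gap is at most half a point out of 10. With an SD of 1 or 2 points the gain is slight. This also stands.

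*Randomisation already protects the comparison.* A reader might infer that unstratified allocation would bias the result. It would not: overall type I error is near 5%. Covariate adjustment can recover most of the precision and may be specified in an analysis plan that is not shown. Its absence from the protocol is therefore not a fault in itself. The allocation factor is different, since it has to exist before the first randomisation.

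*Read together, Sections 5.1 and 8.1 may agree.* They use nearly the same term, and the list may have been meant to define it. A reader might instead infer that every outpatient hysteroscopy is admitted, including women with no dilatation score. The documents do not settle the first point. They say nothing of women who need no dilatation, and pain at dilatation is a planned measurement. Only the ambiguity can be claimed.

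**Conclusion.** The point holds as a specification gap with modest statistical consequences. Section 8.3 contains an unfinished instruction, no stratification factor is fixed, and Sections 5.1 and 8.1 need reconciling. None of these three statements depends on an assumption.

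The size does. It rests on equal arms of about 24 before dropout, an ablation share near 27%, and a Novasure-Myosure gap that carries over to Thermablate and to both arms. On those terms a 95%-extreme imbalance moves the arm difference by about 0.10 to 0.13 points. The power to be gained is about 9 to 13 percentage points with the printed SDs and about 0 to 2 with an SD of 1 to 2 points. What is at risk is precision, and the credibility of a single small trial should the arms turn out unequal in procedure. The trial's validity is not in question on this ground. The change is still worth making, because it costs little and cannot be made to the allocation list once recruitment has begun.

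**What to change.** 1. In Section 8.3, replace the note with a statement that randomisation is 1:1 and stratified by planned procedure: Myosure v endometrial ablation, plus an 'other' stratum if the wider population is intended. Name the method that keeps the arms balanced within each stratum, since simple randomisation inside strata would achieve nothing.
2. In Section 6, state that the pain-score comparison includes procedure type as a covariate, or refer to the analysis plan if it already says so.
3. Reconcile Sections 5.1 and 8.1 so that both state the same population, and make clear whether the list of three procedures is complete. Which population is intended is for the sponsor to decide.

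The cost is protocol wording, a two- or three-stratum allocation list and one extra model term.
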